15.2 Spectral Domain Optical Coherence Tomography (SD-OCT)

Retinal anatomy will be evaluated by SD-OCT scans of both eyes once at the screening visit, twice at the baseline visit, and once at 1, 2, 3, 6, 9 and 12 months after study agent administration and at each long-term follow-up visit. Additional SD-OCT scans may be obtained at the discretion of the investigator. Each SD-OCT will generate macular volume scans and high resolution horizontal and vertical scans centered on the fovea.

The observed and change from baseline (average of the two baseline results) values for continuous SD-OCT parameters will be summarized for each eye using continuous descriptive statistics by visit for each group and for all subjects. In addition, percent change from baseline will be summarized for Cystic Cavity Volume (mm^3). The paired t-tests and graphs as specified in Section 15.1 will be created for all OCT parameters and two-sample t-tests comparing study eye with fellow eye will be performed only for Cystic Cavity Volume (mm^3). SD-OCT parameters include: Cystic Cavity Volume (mm^3), Macular Volume (mm^3), Central Segment (μ m), Inner Circle Superior (μ m), Inner Circle Nasal (μ m), Inner Circle Inferior (μ m), and Outer Circle Temporal (μ m). Categorical parameters will be summarized using counts and percentages for each group and for all subjects at each visit for each eye. Categorical parameters include: Ellipsoid zone evaluation over fovea, RPE disruption, is the EZ band present within the scans, were the scans obtained in follow up mode, was manual segmentation performed. A subject listing of SD-OCT results will also be produced.

15.4 Microperimetry

Microperimetry testing will be performed using the MP1 microperimeter once at the screening visit, twice at the baseline visit, once at 1, 2, 3, 6, 9, and 12 months after study agent administration, and once at each long-term follow-up visit.

The observed and change from baseline (average of the two baseline results) values for continuous microperimetry parameters will be summarized for each eye using continuous descriptive statistics by visit for each group and for all subjects. The paired t-tests and figures as specified in Section 15.1 will be created. Continuous microperimetry parameters for include: Bivariate Contour Ellipse Area (BCEA) 95% Fixation Points (square degrees), Mean Sensitivity, Mean Defect, Percentage of Fixation Points within 2 Degrees, Percentage of Fixation Points within 4 Degrees, Percentage of Fixation Points Located Centrally, and Duration Time for Grid Testing; and Duration Time and BCEA 95% Fixation Points (Square Degrees) for 30 Second Fixation Test. Categorical parameters will be summarized using counts and percentages for each group and for all subjects at each visit for each eye. Categorical parameters include: fixation stability (Stable, relatively unstable, and unstable) and fixation location (predominantly central or predominantly eccentric). Percentages will be based on the number of subjects with responses. A subject listing of microperimetry results will also be produced.

15.5 Reading Speed

Reading speed will be performed once at the screening visit, twice at the baseline visit, and once at 3, 6, 9, and 12 months after study agent administration, and at each long-term follow-up visit. Reading speed will be measured using University of Minnesota trademark for low vision visual acuity (MNREAD) charts.

Reading Acuity (RA) is the smallest print size that the patient can read without making significant errors. RA is calculated as 1.4 - (sentences read x 0.1) - (number of words read incorrectly x 0.01), a method proposed by Patel et al².

Critical Print Size (CPS) is the smallest print size that supports reading speed at \ge 80% of the mean reading speed at the preceding print sizes. Maximum Reading Speed (MRS) is the mean reading speed for all print sizes larger than the CPS.

The observed and change from baseline (average of the two baseline results) reading speed results (Maximum Reading Speed [WPM], Reading Acuity, Critical Print Size) will be summarized using continuous descriptive statistics by visit for each group and for all subjects. The paired t-tests and figures as specified in Section 15.1 will be created. A subject listing of reading speed results will also be produced.

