#### 10.7.3 Efficacy Analysis

Efficacy will be measured by evaluation of visual acuity, schisis cavity volume on OCT scans, static and kinetic visual fields measured using the Octopus perimeter, microperimetry, reading speed, contrast sensitivity, ERG, and quality of life questionnaires.

Visual acuity data will be presented as the ETDRS letter score at each time point.

Volumetric analysis of schisis cavity size will be quantified using a method developed at the Casey Eye Institute.

For visual fields, mean sensitivity, mean defect, square root of the loss variance, volume of full field hill of vision, 30 degree hill of vision, total volume loss, the area of kinetic perimetry isopters in mm^2, and the mean luminance sensitivity for the entire test field in decibel steradians, will be recorded for each eye and at each time point.

CONFIDENTIAL

For microperimetry, the equivalent of the 10-2 stimulus pattern will be used with a Nidek MP-1, microperimeter. The initial analysis will evaluate total sensitivity over time. Subsequent analyses will evaluate focal regions of change or point-by-point regression over time.

For reading speed, the reading acuity, critical print size and maximum reading speed will be recorded.

For contrast sensitivity, the number of letters read will be recorded.

The ffERGs responses will be analyzed by recording amplitude and implicit time measurements for each eye for standard ISCEV responses. Additional analyses to isolate the rod-only b-wave response may also be performed.

The mfERG responses will be analyzed by recording average latency and amplitudes for each of 6 standard rings for a 103 hexagon display.

Quality of life questionnaires will be scored using the NEI VFQ-25 scoring algorithm.

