14 July 2017	6.0	Revised estimated study enrollment duration in the Protocol Summary and Section 3.
		Revised estimated number of participants in the Protocol Summary and Sections 3, 4, and 10.2.
		Modified the study design to include Group 2A throughout the protocol. Participants in this group will be 6-17 years old and receive the study agent at the middle dose.
		Added clarifications for the MTD throughout the protocol.
		Updated section 1.3.1 to further clarify risks related to the use of steroids.
		Added risks associated with anesthesia to section 1.3.1.
		Revised Sections 4.1 and 10.3 to include the new Group 2A and to clarify the washout period for CAIs.
		Updated Exclusion Criteria # 3 (section 4.3).
		Added clarification to Section 7.2.1.5 regarding SAE definition.
		Fixed minor typographical and formatting errors.

Date	Protocol Version	Summary of Changes
12 January 2018	7.0	Added risks associated with the study in Section 1.3.1. Added "Ocular Fluids" Section 6.5. Clarification added to the Storage of Samples for Future Research in Section 13.7.
21 October 2019	8.0	Removal of efficacy testing at LTFU visits: 12 month analysis revealed that AGTC-301 is generally safe and well-tolerated, but has no evidence of a treatment effect. Addition of LTFU questionnaire in Appendix B Updated publication policy

# SITE-SPECIFIC APPENDIX 1

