15.1 Visual Acuity

BCVA testing will be performed once at the screening visit, twice at the baseline visit, and once at each visit after study agent administration, including each long-term follow-up visit. BCVA will be determined using a standard ETDRS visual acuity testing protocol.

The observed and change and percent change from baseline (average of the two baseline results) visual acuity will be summarized for each eye using continuous descriptive statistics by visit for each group and for all subjects. P-values from paired t-tests comparing post-baseline visits with baseline visit and p-values from 2-sample t-tests comparing study eye with fellow eye will be presented for Treatment Groups 2A, 2+2A, 4, 3+4, and all subjects combined. All inferential statistics are

exploratory in nature. Visual acuity data will be presented as the letter score and the logMAR (calculated as (85-ETDRS)/50, where ETDRS is the ETDRS/EVA letter score) at each time point. Change from baseline in ETDRS letter score will be summarized for the following categories: <=-15, -15 to <-8, -8 to <0, no change, >0 to 8, >=8 to 15, >=15. A subject listing of visual acuity will also be produced.

Box plots of change from baseline in ETDRS BCVA by visit will be presented by group and overall (one box for each group side-by-side at each visit) and repeated by eye (study eye and fellow eye).

Line plots of ETDRS BCVA letter score by visit with 95% confidence intervals (CIs) will be plotted by group and overall. Right and left eyes will be displayed side-by-side on the same page.

Histograms of ETDRS BCVA score at each visit by group and overall will be presented in panel graphs (one panel for each group by visit) and repeated by eye (study eye and fellow eye).

08 August 2017

Scatter plots of ETDRS BCVA score at follow-up visits versus baseline (also known as shift plots) by group and overall will be presented in panel graphs (one panel for each group by visit) and repeated by eye (study eye and fellow eye). A regression line and a line going through the origin will be overlaid in the scatter plots.

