Listing 16.2.8.3	Coagulation Results
Listing 16.2.9	Immunology Result
Listing 16.2.10	Vector Analysis Results
Listing 16.2.11	Slit Lamp Examination
Listing 16.2.12	Tonometry
Listing 16.2.13	Indirect Ophthalmoscopy
Listing 16.2.14	Long-Term Follow-Up Information
Listing 16.2.15	Investigator Comments

24. Figures

Figure Number	Title
Best-corrected Visual Acuity Score	
Figure 14.2.1.1.1	Box Plot of Change from Baseline in ETDRS Best-corrected Visual Acuity Score – Study Eye
Figure 14.2.1.1.2	Box Plot of Change from Baseline in ETDRS Best-corrected Visual Acuity Score – Fellow Eye
Figure 14.2.1.2.1	Histograms of ETDRS Best-corrected Visual Acuity Score – Study Eye
Figure 14.2.1.2.2	Histograms of ETDRS Best-corrected Visual Acuity Score – Fellow Eye
Figure 14.2.1.3.1	Shift Plots of ETDRS Best-corrected Visual Acuity Score – Study Eye
Figure 14.2.1.3.2	Shift Plots of ETDRS Best-corrected Visual Acuity Score – Fellow Eye
Figure 14.2.1.4	Line Plots of ETDRS Best-corrected Visual Acuity Score
Static Perimetry: 3	0 degree Hill of Vision (decibel steradians), Volume of full field Hill of
Vision (decibel ste	radians), Total Volume Loss (decibel steradians), Reliability Factor
Figure 14.2.2.1.1	Box Plot of Change from Baseline in Static Perimetry – Study Eye
Figure 14.2.2.1.2	Box Plot of Change from Baseline in Static Perimetry – Fellow Eye
Figure 14.2.2.2.1	Histograms of Static Perimetry – Study Eye
Figure 14.2.2.2.2	Histograms of Static Perimetry – Fellow Eye
Figure 14.2.2.3.1	Shift plots of Static Perimetry – Study Eye
Figure 14.2.2.3.2	Shift plots of Static Perimetry – Fellow Eye
Figure 14.2.2.4	Line Plots of Static Perimetry
OCT: Cystic cavity volume (mm [^] 3), Macular volume (mm [^] 3), Central segment (μm),	
Inner circle superior (μ m), Inner circle nasal (μ m), Inner circle inferior (μ m), Inner circle	

(μm), and Outer circle temporal (μm)	
Figure 14.2.3.1.1	Box Plot of Change from Baseline in OCT – Study Eye
Figure 14.2.3.1.2	Box Plot of Change from Baseline in OCT – Fellow Eye
Figure 14.2.3.2.1	Histograms of OCT – Study Eye
Figure 14.2.3.2.2	Histograms of OCT – Fellow Eye
Figure 14.2.3.3.1	Shift Plots of OCT – Study Eye
Figure 14.2.3.3.2	Shift Plots of OCT – Fellow Eye
Figure 14.2.3.4	Line Plots of Change from Baseline in OCT
Reading Speed: Maximum Reading Speed, Reading Acuity, Critical Print Size	
Figure 14.2.4.1	Box Plot of Reading Speed – Both Eyes
Figure 14.2.4.2	Histograms of Reading Speed – Both Eyes

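### The SAP's reading-acuity formula subtracts misread words on a scale where lower is better, so errors improve the score

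*SAP*

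**What the plan says.** SAP 15.5 first describes the measure: "Reading Acuity (RA) is the smallest print size that the patient can read without making significant errors". It then gives the scoring rule: "RA is calculated as 1.4 - (sentences read x 0.1) - (number of words read incorrectly x 0.01"), and attributes it to a cited MNREAD test-retest study.

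On use, the section states that observed and change-from-baseline "reading speed results (Maximum Reading Speed [WPM], Reading Acuity, Critical Print Size) will be summarized using continuous descriptive statistics", by visit and group, with baseline taken as the average of two results. It adds the paired t-tests and figures of SAP 15.1, where all inferential statistics are labelled exploratory. RA therefore enters Tables 14.2.5.1 and 14.2.5.2, the reading-speed listings, and the figures that SAP section 24 lists under "Reading Speed: Maximum Reading Speed, Reading Acuity, Critical Print Size".

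The protocol gives no scoring rule. Its section 10.7.3 says only: "For reading speed, the reading acuity, critical print size and maximum reading speed will be recorded". The SAP introduction states that the SAP's methods replace those of the protocol, and SAP section 19 lists no change to RA scoring. The printed formula is thus the only instruction a programmer has.

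**The concern.** The definition and the formula disagree about errors. A smallest readable print size is better when it is smaller, and the sentence term follows that direction. The error term carries the same sign as the sentence term, so a misread word earns credit, as a sentence read does, at one tenth of the weight. A measure defined by reading without significant errors should not improve as errors increase.

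If the formula was programmed as printed, observed RA is wrong at every visit with at least one error. Change in RA is wrong for every patient whose error count changes. In some patients a decline would be reported as a gain, or the reverse.

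**Working it through.** **Inputs.** From SAP 15.5: constant 1.4, weight 0.1 per sentence read (S), weight 0.01 per word read incorrectly (E). The documents report no values of S or E, so those below are illustrations. There is no stated RA figure to reproduce.

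**Formulas.**
- As written: W = 1.4 - 0.1·S - 0.01·E
- Errors penalised: C = 1.4 - 0.1·S + 0.01·E
- Difference: W - C = -0.02·E

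**Level of RA at S = 10.**

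| E | W | C |
|---|---|---|
| 0 | 0.40 | 0.40 |
| 1 | 0.39 | 0.41 |
| 5 | 0.35 | 0.45 |
| 10 | 0.30 | 0.50 |
| 20 | 0.20 | 0.60 |

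As written, RA improves with every error. Ten sentences with ten errors score 1.4 - 1.0 - 0.10 = 0.30, the same as eleven sentences with none (1.4 - 1.1 = 0.30). With errors penalised the two cases score 0.50 and 0.30.

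**Change from baseline.** Write dS and dE for the changes in sentences and errors.
- As written: -0.1·dS - 0.01·dE
- Errors penalised: -0.1·dS + 0.01·dE
- Difference: -0.02·dE, which is zero when the error count does not change

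The product of the two changes is 0.01·dS² - 0.0001·dE². It is negative, meaning opposite directions, exactly when |dE| > 10·|dS|. Below that limit the direction is right but the size is wrong unless dE = 0.

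| Baseline to follow-up | As written | Errors penalised | Effect |
|---|---|---|---|
| S 10 to 10, E 2 to 10 | -0.08 | +0.08 | reversed |
| S 10 to 9, E unchanged | +0.10 | +0.10 | none |
| S 10 to 9, E +5 | +0.05 | +0.15 | worsening understated |
| S 10 to 9, E +10 | 0.00 | +0.20 | worsening hidden |
| S 10 to 9, E +11 | -0.01 | +0.21 | reversed |
| S 10 to 11, E +5 | -0.15 | -0.05 | gain overstated |

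Averaging two baselines does not help. Take S = 10 throughout, baseline errors 2 and 4, and follow-up errors 8:
- As written: baseline (0.38 + 0.36)/2 = 0.37, follow-up 0.32, change -0.05
- Errors penalised: baseline (0.42 + 0.44)/2 = 0.43, follow-up 0.48, change +0.05

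**Group means.** A mean shift of 1, 3 or 5 errors moves mean RA change by 0.02, 0.06 or 0.10. The last equals one whole sentence step. One patient with 8 more errors at unchanged S is mis-scored by 0.16, which moves the mean by 0.16/3 = 0.053 in a group of three and by 0.16/6 = 0.027 in a group of six.

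**The case against.** Four points can be made against this.

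1. **One character.** The point turns on a single sign, which could be a misprint or a conversion slip. That is possible but not shown: plus signs print correctly elsewhere in the SAP, for instance in the group labels 2+2A and 3+4. Looking at the approved SAP page would settle it.

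2. **Another element may be the faulty one.** The SAP does not define sentences read. If only error-free sentences count, the fault remains: at S = 9, three errors give 0.47 against 0.50 with none. If the last term was meant to credit words read correctly in a partly read sentence, the minus would be right and the word incorrectly would be the slip. The printed formula would still be wrong. What stands is that the documents prove a contradiction but do not prove which element to change. The 0.02 per error assumes that errors should be penalised at the printed weight.

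3. **Reversals need large changes in errors.** This holds once the sentence count changes, because more than ten words per sentence are then required. It does not hold when the sentence count is unchanged, where any change in errors reverses the direction, though a one-word change gives an error of only 0.02.

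4. **Limited reach.** RA is one of three reading results within one of nine secondary variables, and the tests are exploratory. Critical print size and maximum reading speed do not use the formula. This is correct, and it limits the weight of the point.

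**Conclusion.** The concern holds. As printed, SAP 15.5 rewards misread words on a scale where lower is better, and nothing else in the documents corrects this. The mis-score is 0.02 per error in the level of RA and -0.02 times the change in errors in change from baseline. Direction reverses only when |dE| > 10·|dS|.

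This rests on two premises: that lower RA is better, which follows from the definition and the sentence term although the SAP does not say so in words, and that errors should count against the patient. How far any reported result is affected depends on the error counts and on what was programmed, and the documents show neither.

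It should be fixed, because it is a definite error in a reported secondary efficacy result. It does not touch the primary safety analysis or dose escalation.

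**What to change.** In SAP 15.5, write RA = 1.4 - (sentences read × 0.1) + (number of words read incorrectly × 0.01), and state what counts as a sentence read. Before issuing the change, check it against the approved SAP page, the cited MNREAD test-retest study and the RA program.

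The text change is one sign. The protocol's change log for version 8.0 shows that an analysis has already been run: "12 month analysis revealed that AGTC-301 is generally safe and well-tolerated, but has no evidence of a treatment effect". If the printed formula was used there, RA must be re-derived and the RA rows of Tables 14.2.5.1 and 14.2.5.2, the reading listings and the RA figures re-run. If the program already penalises errors, only the text needs correcting.

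A separate wording note, which adds nothing to the weight of this point: the letter-change categories in SAP 15.1, "<=-15, -15 to <-8, -8 to <0, no change, >0 to 8, >=8 to 15, >=15", read literally place -15, +8 and +15 in two categories each. One line removes the overlap: <=-15, >-15 to <-8, -8 to <0, 0, >0 to <8, >=8 to <15, >=15.

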4.1 General Study Design

This is a non-randomized, open-label, Phase 1/2 dose escalation study of the safety and efficacy of rAAV2tYF-CB-hRS1 administered by intravitreal injection in one eye in individuals with XLRS. The primary objective is to evaluate safety and the secondary objective is to evaluate efficacy.

Each participant is to receive rAAV2tYF-CB-hRS1 by intravitreal injection in one eye on a single occasion as outlined in the schematic below.

		Number of Dose Level				
Group ^a	Age (yr)	Subjects	vg/mL	Volume	vg per eye	
1A	≥ 18	3	1.43 × 10 ¹²	0.07 mL	1 × 10 ¹¹	
1B	≥ 18	3	1.43 × 10 ¹²	0.07 mL	1 × 10 ¹¹	
2	≥ 18	3	4.3 × 10 ¹²	0.07 mL	3 × 10 ¹¹	
2A	6-17	Up to 6	4.3 × 10 ¹²	0.07 mL	3 × 10 ¹¹	
3	≥ 18	3	4.3 × 10 ¹²	0.14 mL	6 × 10 ¹¹	
4	≥ 6	Up to 15	MTD ^b	MTD	MTD	

Schematic of Study Design:

^a Visual acuity not better than 58 Early Treatment Diabetic Retinopathy Study (ETDRS) letter score in Group 1A, 63 in Groups 1B, 2, 2A & 3, 68 in Group 4.

^b MTD = maximum tolerated dose determined in Groups 1A, 1B, 2 and 3 for adults, in Groups 1A, 1B, 2, and 3 (adult participants only) and 2A (pediatric participants only) for pediatric participants.

Participants in Groups 1A, 1B, 2 and 3 are at least 18 years of age and receive the vector at a lower dose (Groups 1A and 1B), middle dose (Group 2) or higher dose (Group 3). Participants in Group 1A have visual acuity that is worse than participants in subsequent groups (ETDRS letter score of 58 in Group 1A and 68 in other groups). Participants in Group 2A will be 6-17 years of age and receive the

vector at the middle dose level. Participants in Group 4 will be at least 6 years of age and will receive the vector at the maximum tolerated dose (MTD) determined in Groups 1A, 1B, 2, and 3 for adults; in Groups 1A, 1B, 2, and 3 (adult participants only) and 2A (pediatric participants only) for pediatric participants.

Participants in all groups are selected from individuals who are not being treated with a carbonic anhydrase inhibitor during the study and have not been treated with any carbonic anhydrase inhibitor within the 3 months prior to enrollment in the study. Participants are asked not to begin treatment with a carbonic anhydrase inhibitor within 6 months after study agent administration.

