9.4 Data Analysis Conventions

All data analysis outlined in this SAP will be performed by Statistics & Data Corporation (SDC). Statistical programming and analyses will be performed using SAS[®] Version 9.4 or higher. Output will be provided in Rich Text Format (RTF) for tables and figures and Portable Document Format (PDF) for tables and listings using landscape orientation. All study data for treated subjects will be listed by group, subject, and visit (as applicable) unless otherwise specified. Only a disposition listing will be created for screen failed subjects.

Summaries for continuous and ordinal variables will include the number of observations (n), arithmetic mean, standard deviation (SD), median, minimum, and maximum. Minima and maxima will be reported with the same precision as the raw values; means and medians will be presented to one additional decimal place than reported in the raw values. Standard deviations will be presented to two additional decimal places than reported in the raw values. Summaries for discrete variables will include frequency counts and percentages. All percentages will be rounded to one decimal place (i.e., XX.X%). Change from baseline will be calculated as follow-up visit values minus the baseline value.

All statistical tests will be two-sided with alpha level of 0.05. Unless otherwise specified, summaries will be presented by group (1A, 1B, 2, 2A, 2+2A, 3, 4, 3+4, and all subjects) and, where appropriate, visit.

Unscheduled visits will not be summarized. Study visits will be referred to in all tables and listings with the expected study day/month/year corresponding to the visit to enable reviewers to understand the assessment timing without referring to the protocol visit schedule. The following table shows the scheduled study visits, their planned study day:

Scheduled Visit	Planned Study Day
Visit 1	Screening
Visit 2	Baseline
Visit 3	Day 0
Visit 4	Day 1
Visit 5	Day 7
Visit 6	Day 14
Visit 7	Month 1
Visit 8	Month 2
Visit 9	Month 3
Visit 10	Month 6
Visit 11	Month 9
Visit 12	Month 12
Visit 13	Year 2
Visit 14	Year 3
Visit 15	Year 4
Visit 16	Year 5
1	

10. Disposition of Subjects

The following disposition items will be summarized:

- The number of subjects screened (who signed the informed consent/assent form)
- The number of screen failures
- The number of subjects enrolled (who met the enrollment criteria)
- The number of subjects treated (who received an intravitreal injection of study agent)

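### SAP 15.5 tests children's reading speed before against after treatment with no reference for growth in reading skill, so these exploratory p-values can show a benefit without any retinal effect

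*SAP*

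**What the plan says.** SAP 15.5 lists three reading results, "Maximum Reading Speed [WPM], Reading Acuity, Critical Print Size", measured twice at baseline (averaged) and at Months 3, 6, 9 and 12. The SAP adds long-term visits, but the current protocol's schedule stops reading speed at Month 12. The inferential plan is one sentence: "The paired t-tests and figures as specified in Section 15.1 will be created".

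Section 15.1 defines these as "P-values from paired t-tests comparing post-baseline visits with baseline visit", and they "will be presented for Treatment Groups 2A, 2+2A, 4, 3+4, and all subjects combined". SAP 9.4 sets the level: "All statistical tests will be two-sided with alpha level of 0.05".

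On age, SAP 4.1 says: "Participants in Group 2A will be 6-17 years of age". That group has up to 6 participants, and Group 4 is open from age 6.

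On the measure, SAP 15.5 says: "Maximum Reading Speed (MRS) is the mean reading speed for all print sizes larger than the CPS". CPS is the critical print size.

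Section 15.5 names no age norm, age covariate, natural-history comparison or study-eye against fellow-eye test. Sections 15.1 to 15.3 name a fellow-eye test where one is wanted.

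**The concern.** Maximum reading speed is taken at print sizes above the critical size, where print size is no longer the limit. What remains includes reading fluency. A child of primary-school age can be expected to read faster after a school year whatever happens in the retina. That is general reasoning and not a figure from the documents, and the effect should be largest in the youngest children.

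The trial is single-arm. The two baseline measurements are made at one visit within 7 days before dosing, so they cannot estimate a yearly trend. A before-after test therefore adds growth in literacy to any drug effect. The error runs in one direction, toward benefit. At stake is how the pediatric reading-speed p-values, and the pooled ones that include children, are interpreted.

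**Working it through.** **The plan's own figures.** The plan gives no effect size, SD or power for reading speed. Its only computed figures are the upper limits for the dose-limiting toxicity rate. These reproduce (1 - 0.025^(1/9) = 33.63%; 1 - 0.025^(1/27) = 12.77%) but do not bear on this point.

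**Inputs from the documents.** n = 6, the maximum in Group 2A (SAP 4.1); two-sided 0.05 (SAP 9.4); paired test of each post-baseline visit against baseline (SAP 15.1, 15.5).

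**Assumptions, not in the documents.** No drug effect; mean growth g of 5, 10 or 20 words per minute over 12 months; SD of the change s of 15, 20 or 30.

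**Formula.** The critical value is t(0.975, 5 df) = 2.571, so an observed mean gain above 2.571/√6 = 1.05 SD is significant. The test statistic is noncentral t with 5 df and noncentrality (g/s) × √6. For g = 10 and s = 15 this is 0.667 × 2.449 = 1.63, giving a rejection probability of 27%.

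**Probability of a significant result at Month 12, n = 6:**

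| SD of change | g = 5 | g = 10 | g = 20 |
|---|---|---|---|
| 15 | 10% | 27% | 74% |
| 20 | 8% | 17% | 51% |
| 30 | 6% | 10% | 27% |

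Without growth the figure would be 5%, of which 2.5% is in the direction of benefit. With growth, most rejections are in that direction. An even chance at one visit needs mean growth of about one SD of the change (ratio 1.0 gives 50.7%).

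**Earlier visits.** If growth is linear, Months 3, 6 and 9 carry 25%, 50% and 75% of g. With SD 15 and g = 5, 10 or 20, the figures are 5%, 6% and 10% at Month 3; 6%, 10% and 27% at Month 6; and 8%, 17% and 51% at Month 9.

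**Any of the four visits.** A simulation of 40,000 trials used a two-test baseline, linear growth and a between-child slope SD of half the mean slope. At least one significant gain appears in about 9% of trials with no growth. With growth of 10 words per minute per year it appears in 25% (measurement SD 20) to 50% (SD 10).

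**Dilution by adults.** As an illustration, put 6 children among 27 subjects with no change in adults. The mean shift is g × 6/27 = 1.1, 2.2 or 4.4 words per minute. Simulated with SD 15, the test is significant in about 6%, 10% and 22% of trials. The share of children in Group 4 is not fixed, so the true dilution is unknown.

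**The case against.** The strongest reply is that the SAP already limits these p-values. Section 15.1 calls all inferential statistics exploratory, efficacy is a secondary objective, reading speed is one of nine secondary variables, and enrolment in later groups depends on safety review. Uncontrolled before-after testing is also a limit of every efficacy measure in a single-arm trial. The protocol's change log for version 8.0 reports no evidence of a treatment effect at 12 months. All of this stands and lowers the severity. It does not remove the bias, which is more specific here than elsewhere because the measure itself includes a skill that children are still acquiring.

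A reader might infer three stronger things that the documents do not support:

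- **That schooling will produce a significant result.** Growth and SD are both assumed, the age mix within 6-17 is not fixed, and at SD 30 with growth of 5 the inflation is only from 5% to 6%.
- **That the near-certain result for larger samples applies.** With 12 children, SD 15 and growth of 20 the same formula gives 99%. No planned row has that composition unless Group 4 were 12 children and no adults.
- **That reading acuity and critical print size are safe substitutes in children.** SAP 15.5 scores reading acuity from sentences read and words misread, and derives critical print size from reading speed. Neither is shown to be free of literacy. As printed, the acuity formula also subtracts for misread words, so errors move the score the same way as sentences read.

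Protocol 6.10 says visual function is measured in both eyes, which could supply an internal reference. But SAP 15.5 plans no contrast between eyes for reading, and three of its four reading-speed figures are titled Both Eyes. Whether by-eye data exist is unclear.

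**Conclusion.** The point holds as a minor one. The planned before-after p-values for maximum reading speed in Group 2A, and in any row that includes children, cannot separate a visual effect from growth in reading skill, and they err toward benefit. At Month 12 with 6 children, the chance of a significant result without drug effect ranges from 6% (growth 5, SD 30) to 74% (growth 20, SD 15). It is smaller at Months 3 to 9 and, in the all-subject row, diluted by adults.

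That range rests wholly on assumed growth and SD. The design facts do not: raw words per minute, ages 6-17, a paired test, and no reference for growth are all in the SAP. The severity is minor because the statistics are exploratory and no decision depends on them.

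**What to change.** In SAP 15.5:

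1. Report maximum reading speed in participants under 18 by listings and descriptive statistics only.
2. Give no paired-test p-value for 2A or 2+2A. The adult part of 2+2A is Group 2 alone, n = 3, which Section 15.1 does not list for testing.
3. Restrict the Group 4, 3+4 and all-subject tests to adults, and label them so.
4. State that change in words per minute in children is not by itself evidence of effect.
5. Do not present reading acuity or critical print size as free of literacy effects in children.
6. Reconcile Protocol 6.10 (both eyes measured) with the Both Eyes figure titles. If reading is tested in each eye separately, a within-child study-eye minus fellow-eye change may be tested instead, since growth in literacy largely cancels.

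If growth cancels fully, the chance of a false benefit at one visit returns to 2.5%. If a quarter of a growth of 10 to 20 words per minute remains, it is 3.7% to 16.9% (SD of change 30 down to 10).

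The cost is SAP wording and fewer p-values, with no new data. The downside is that there is no before-after test of reading speed in children.
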